15. Revision of the statistical analysis section (i) to group all details in a single place to facilitate readability of it and (ii) clarify some requirements.
 - Statistical analysis methodology restructured and clarification added to explain that results from Part A (Phase I and Phase IIa), Part B and Part C will be summarised separately due to differences in study design, dose regimens and patient populations. However analyses in specific populations and for specific dose regimens may be performed in the overall study population.
 - Efficacy endpoint definitions moved to the statistical section only, removing the duplicate definitions from Section 5.6 and removing Section 12.4 from protocol Version 14; Section 14.1.7. There is no change in the definitions and no loss of information.

- Timing of analyses for Part B more clearly identified. Clarification added that the statistical analysis would be fully described in a Statistical Analysis Plan (SAP) prior to database lock; [Section 14.1.5](#).
 - “Not evaluable” added as an option for tumour response for completeness; [Section 14.1.7](#).
 - Requirement to present the primary endpoint at each timepoint removed as not necessary; [Section 14.1.7](#).
 - Handling tumour response data from patients who withdraw or are lost to follow-up as disease progression at the time of the last assessment removed; [Section 14.1.12](#). These data will be handled as censored data and relevant sensitivity analyses will be conducted.
 - Clarifications added to the definitions of the efficacy endpoints and of analysis of time-to event endpoints; [Section 14.1.7](#).
16. Addition of a new section on collection of IMP dosing errors previously omitted; [Section 16.3.6](#).

Further changes to improve sense, readability and prevent misunderstanding have also been made *without changes to overall protocol requirements*:

17. Clarifications to the rationale for a lower dose of Betalutin for patients with prior autologous-SCT and/or lower platelet counts, including the consolidation of text previously in the study design section; [Section 4.8.11](#). There is no change to the rationale previously described in Version 14.
18. Clear presentation of the design of each part of the study and of the assessments to be performed. Where procedures differ between different parts of the study, these have been separated; [Section 6.1](#).

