Open label phase IIa expansion cohort to enable the collection of samples for Betalutin pharmacokinetics and total lilotomab antibodies pharmacokinetics in at least 10 patients (up to a maximum of 20 patients) receiving the “40/15” regimen.

Figure 6-1 ` LYMRIT 37-01 Study Design (Part A, Part B and Part C)

- Part A is closed to enrolment.
- Part B (PARADIGME) is open to enrolment for patients with FL.
- Part C (Pharmacokinetic Cohort) is open at selected sites (subject to regulatory and EC/IRB Approvals) to enrolment for patients with iNHL. All patients will receive the “40/15” regimen. Patients entering Part C will follow the same Schedule of Assessments (except QoL) as those in Part B.

Definition of study periods:

The *study treatment period* is defined as from the first administration of rituximab pre-treatment until 12 weeks after Betalutin administration. All patients will be closely monitored during the study treatment period.

The *follow-up period* is

Part A - up to 5 years or until the first anticancer treatment after Betalutin administration. Survival and potential long-term toxicity information will continue to be collected up to 5 years, even after further anticancer treatment has begun. All patients will be followed closely the first year after treatment, thereafter every 6 months (See [Section 6-3](#) Schedule of Assessments).

Part B and Part C - up to 5 years after Betalutin administration.

Extensive follow-up (hospital visits) will take place for all patients every 3 months for the first year (Months 6, 9 and 12). Tumour imaging assessments are only required until the patient has further anticancer treatment after Betalutin administration or disease progression prior to further anticancer therapy as assessed by central imaging review. All other scheduled assessments should be performed.

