12 EFFICACY ASSESSMENTS

Contrast enhanced CT and PET/CT scans will be evaluated at the study centre(s).

For **Part A (phase I and phase IIa)**, tumour response will be determined by investigator assessment. Cheson criteria Versions 1999 and 2007 will be applied (35, 36).

For **Part B (FL phase IIb) and Part C (Pharmacokinetic Cohort)**, investigator assessment will initially be applied as a measure for assessment of tumour response and any urgent patient management decisions. Tumour response will also be determined by independent central review and this assessment used as a basis for all protocol guidelines for management of the patient related to disease progression status. In presence of disease progression per investigator assessment, tumour assessments should continue until disease progression is documented by independent central review, unless an urgent patient management decision is required. All urgent patient management decisions will be documented. Cheson criteria Version 2014 will be applied (40).

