Category	Data	Comments
Demography and baseline information	Demographics	
	Disposition	
	Eligibility	Includes reasons for screening failure
	Med history	diagnosis of NHL (part C patients)
	Med history	diagnosis of FL (part B patients)
	Med history	general med history, listing only, no summaries required
	Prior and con meds	Prior meds, listing only, no summaries required
	Prior and con meds	Previous treatment for FL (part B), iNHL (part C)
Efficacy endpoints to be summarised are: ORR, CRR, DoR, DoCR and PFS from IRC assessment	Tumour visit response	From IRC: ORR, CRR, DoR, DoCR, PFS
Exposure data	Exposure	
Safety (AE and laboratory data) data	AE	
	Biochem	Listings only, no summaries required

	Haematology	Both listings and summaries required
--	-------------	--------------------------------------

OS variables will not be derived.

For all other data no formal TFL outputs are required. For all data in the table below, SAS datasets of the raw data should be supplied to Nordic Nanovector.

Table 2: Data for which only SAS raw data sets are required

Data table	Comments
AE SI	
Dna damage	DNA damage (Date/time) is this available?
ECG	ECG data only collected at baseline
Genomic biomarkers	Sample collection for genomic biomarkers
Imaging	Spect/CT evaluation
Immunological assessment	Protein Electrophoresis
Lab test results	Pregnancy test
Phys exam	Physical exam at baseline and through trial
PK concentrations	PK sampling times
Prior and con meds	Previous treatment for iNHL
Prior and con meds	Further anti-cancer therapies
Prior and con meds	Concomitant medications
Prior and con procedures	
Questionnaire	ECOG
Questionnaire	FACT-Lym
Response	Response following CT and PET assessments
SAE	
Serology sample	Sample collection for serology, hep B hep C HIV
Subject characteristics	Confirms randomisation and dose
Tumour identification	Biopsy tumour tissue - sample date, site, slides
Tumour identification	Target lesions (screening & follow-up)
Tumour identification	Non-measurable lesions (screening & follow-up)
Tumour identification	New lesions
Tumour identification	Bone marrow (screening & follow-up)
Tumour identification	PET (screening & follow-up)
Vital signs	Screening & follow-up
Immunological assessment	ADA (Date/time of sample)

Immunological assessment	HAMA (Date/time of sample)
Immunological assessment	Immunoglobulin (Date/time of sample)
Immunological assessment	Lymphocyte (Date/time of sample)

2 Study Design, Objectives and Endpoints

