2.1.1 Visit Structure

The visit structure and the schedule of assessments are detailed in Tables 6-7, 6-8 and 6-9 in the study protocol (Section 6).

In the protocol, the Betalutin administration day is referred to as Day 0. However, for statistical analysis and to be in line with CDISC (Clinical Data Interchange Standards Consortium) requirement, the Betalutin administration day will be defined as study Day 1. See Section 3.3 for more details.

The study treatment period starts with the single dose infusion of rituximab (375mg/m²) 14 days prior to the administration of Betalutin and lasts for 12 weeks after the Betalutin administration for each participant.

The follow-up period starts from 12 weeks (3 months or 92 days) after the first lilotomab/Betalutin administration up to 5 years as follows (see Protocol Section 6.3 Schedule of Assessments for more details):

- Extensive follow-up (hospital visits): for all participants, every 3 months after Betalutin administration for the first year (i.e. Month 3, Month 6, Month 9, and Month 12). In addition, there will be an additional hospital visit at Week 4 and Month 2 after Betalutin administration. Tumour imaging assessments are only required until the participant has disease progression as confirmed by the IRC or further anticancer therapy prior to progression. All other scheduled assessments are performed regardless of disease progression or administration of further therapy.
- After Month 12: follow-up will continue every 6 months up to 5 years after the Betalutin dose.
 - Extensive follow-up (hospital visits) will be performed until the participant has disease progression as assessed by the IRC or further anticancer therapy prior to progression.
 - Survival Follow-up: Thereafter, the participant will continue limited follow up every 6 months for potential long-term toxicity (new onset of Adverse Events of Special Interest (AESIs), Adverse Drug Reactions (ADRs) and study treatment-related Serious Adverse Events (SAEs), Overall Survival, further anticancer treatment and immunogenicity assessment (ADA, if applicable). Unless blood sampling is required for immunogenicity, limited follow-up visits can be performed by telephone.

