3.7.1 Primary Endpoint: Overall Response Rate (ORR) as assessed by IRC assessment

3.7.1.1 Definition of Overall Response Rate (ORR)

A response of CR, PR, Stable Disease (SD), Progressive Disease (PD) and Not Evaluable (NE) is allowed. The response definitions for each category are based on standard criteria and defined in Section 12.3 of the protocol.

If disease assessments for a participant are not available then the response rate for the relevant timepoint will be set to Not Done (ND).

The Overall Response Rate (ORR) is defined as the proportion of participants who achieve a best response of CR or PR at any time. If all disease assessments for a participant are not available then ORR will be set to NE.

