3.7.4 Secondary Endpoint: Progression-free survival (PFS)

3.7.4.1 Definition

PFS is defined as the interval from Betalutin administration and date of:

- Relapse (new or enlarged lesions after CR).
- Progression (new or enlarged lesions after PR or SD).
- Death from any cause.

Documented disease progression is defined as a Relapse (after CR) or progression (after PR or SD) and is indicated at the earliest date when the response assessment is given as progressive disease (PD). Death from any cause includes deaths occurring before the first post-baseline tumour assessment. If death occurs after two or more missed tumour assessments the participant should be censored (see below). PFS for participants meeting the events definition will be derived as follows:

$$\text{Progression-free survival time (months)} = ([\text{earliest of (First date of documented disease progression or death)} - \text{date of Betalutin administration}] + 1) * 12 / 365.25.$$

If none of the above events are observed PFS will be censored as follows:

- Incomplete/no baseline tumour IRC assessments: censor at date of Betalutin administration (study day 1).
- No documented disease progression: censor at date of last tumour IRC assessment where progression was not shown.

- Death or progression after two or more missed tumour assessments: censor at date of last tumour assessment where progression was not shown.

PFS for censored participants will be derived as:

$$\text{Progression-free survival time (months)} = ([\text{Date of censoring} - \text{date of Betalutin administration}] + 1) * 12 / 365.25$$

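### The SAP has no rule for new anticancer therapy started before IRC progression, so IRC-based PFS and duration of response can be overstated with no analysis to show by how much

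*SAP*

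**What the plan says.** **PFS.** SAP 3.7.4.1 counts relapse, progression or death as events. Without an event, the rule is "No documented disease progression: censor at date of last tumour IRC assessment where progression was not shown". A further rule reads "Death or progression after two or more missed tumour assessments: censor at date of last tumour assessment where progression was not shown".

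**DoR and duration of complete response (DoCR).** SAP 3.7.3.1 counts progression or death after response. Responders with neither are censored at their last assessment showing response. None of these definitions mentions new anticancer therapy.

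**When scanning stops.** Protocol 6.1 says "Tumour imaging assessments are only required until the patient has further anticancer treatment after Betalutin administration", or until progression on central review. SAP 2.1.1 agrees: "Tumour imaging assessments are only required until the participant has disease progression as confirmed by the IRC or further anticancer therapy prior to progression". Protocol 12 adds that, after investigator-assessed progression, "tumour assessments should continue until disease progression is documented by independent central review, unless an urgent patient management decision is required". Item 12 of the protocol's amendment rationale describes that exception as meant for patients whose condition needs immediate action at progression.

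**Best response.** SAP 3.7.1.1 defines ORR as the proportion who "achieve a best response of CR or PR at any time". SAP 3.7.2.1 likewise counts a complete response at any timepoint. Neither has a cut-off at new therapy.

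**What is analysed.** SAP 2.3 lists IRC-based efficacy endpoints only. SAP 1 states that OS variables are not derived, and its Table 2 includes "Further anti-cancer therapies" among the data supplied as raw datasets without formal output.

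**The concern.** Kaplan-Meier estimation assumes that a censored patient has the same future risk as those still followed. A patient who leaves scanning because the investigator sees progression and must act is unlikely to meet that assumption. Removing such patients at their last good scan takes failures out of the event count and raises the curve.

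The missed-assessment rule can add to this in PFS. If the patient switches, is no longer scanned and later dies, that death is censored as well once two or more assessments have been missed.

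The quantities at stake are the PFS and DoR percentiles and the 3- to 15-month rates in the close-out report. These are the durability results on which the regimen will be judged. As planned, a reader will see counts of events and censored patients, but the listed outputs do not separate those who switched treatment from those who were event-free at data cut-off.

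**Working it through.** **Reading the rules together**

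1. A patient switches before IRC progression. No further imaging is required (Protocol 6.1, SAP 2.1.1).
2. With no later IRC progression and no death, PFS is censored at the last IRC scan without progression, and DoR at the last scan showing response.
3. If the patient dies after two or more missed assessments, PFS is censored and the death does not count. In DoR the death counts, because that section has no missed-assessment limit. The two endpoints can therefore treat the same patient differently.
4. The sentence introducing the DoR event formula mentions withdrawal, but the event date covers only progression or death. It does not help here, because Protocol 8.1 does not define starting new therapy as withdrawal.

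**Plan figure**

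The plan states no figure for PFS or DoR. The Part B sizing concerns ORR: 87 patients, at least 36 responders, 30% against 48%. It reproduces (exact binomial power 0.911), but has no bearing on this point.

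**Size of the effect on 12-month PFS**

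Inputs:
- Scans at 3, 6, 9 and 12 months (Protocol 14.1.2.2).
- True median m of 6, 9 or 12 months with exponential PFS (assumed).
- Share q of progressing patients who switch before the IRC records progression: 10%, 20% or 30% (assumed).

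True survival per 3-month interval is p = 2^(−3/m), and true 12-month PFS is p⁴. If a share q of those progressing in an interval is censored at its start, the Kaplan-Meier factor becomes p / [1 − q(1 − p)], which is raised to the fourth power.

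Example with m = 9 and q = 0.2: p = 0.7937. The factor is 0.7937 / (1 − 0.2 × 0.2063) = 0.8279, and 0.8279⁴ = 47.0%. The true value is 0.7937⁴ = 39.7%, so the excess is 7.3 points.

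| Assumed median | True 12-month PFS | q = 10% | q = 20% | q = 30% |
|---|---|---|---|---|
| 6 months | 25.0% | 28.2% (+3.2) | 31.8% (+6.8) | 36.1% (+11.1) |
| 9 months | 39.7% | 43.1% (+3.5) | 47.0% (+7.3) | 51.2% (+11.6) |
| 12 months | 50.0% | 53.3% (+3.3) | 56.9% (+6.9) | 60.8% (+10.8) |

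A simulation of 40,000 patients per case agrees. For m = 9 it gives 42.9%, 46.7% and 50.9% against 39.4%.

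**If switching is unrelated to progression**

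In a simulation with m = 9 and about 12%, 24% and 35% of patients switching, the censored estimate is 39.8%, 39.8% and 39.4% against a reference of 39.8%. There is essentially no bias. In the same runs, counting every switch as an event gives 35.9%, 31.6% and 26.6%, which is too low.

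**The case against.** The other side has several good points.

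- **No explicit rule.** A reader might infer that the SAP censors patients when they start new therapy. It does not. The quoted line covers everyone without IRC progression, including those simply event-free at data cut-off. Progression on a later IRC scan, or a death, can still count after a switch. The defect is a missing rule whose effect is censoring.
- **Protocol safeguards.** Scans should continue to IRC progression apart from documented urgent decisions, and IRC review is ongoing (Protocol 16.5). This limits the number affected. It does not remove the group most likely to be failing.
- **No broken promise.** The amendment rationale says "These data will be handled as censored data and relevant sensitivity analyses will be conducted", which could be read as a commitment to this sensitivity analysis. That sentence concerns withdrawal and loss to follow-up, and it stands in a summary of changes. Current Protocol 14.1.12 says only that missing data are not imputed.
- **Best response.** Counting response at any time is not in itself a bias. Protocol 14.1.7 plans best ORR in addition to ORR at 3 months, and defines CRR at any timepoint. What remains is the absent cut-off. Imaging after new therapy is not required, but it is not excluded either. In Protocol 9.6.3.2.1 the Month 6 CT and PET rows lack the restriction shown on the Month 9 and Month 12 CT rows, although the Month 6 overall-response row has it. The IRC charter may deal with this, but it is not among the documents.
- **Limited consequence.** SAP 2.4 states that the terminated study is not powered for its original objectives. PFS and DoR are descriptive. This bears on how serious the gap is, and the estimates will still be reported.

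**Conclusion.** The gap is real and worth closing. Followed as written, the SAP in effect censors patients who leave scanning for new therapy before IRC progression, and in PFS it can censor their later deaths too. IRC-based PFS and DoR can then be too favourable, and the planned outputs do not let a reader judge by how much.

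The size is conditional: about 3 to 12 points on 12-month PFS if 10% to 30% of progressing patients switch first, and essentially nothing if switching is unrelated to progression. Both the share and the underlying median are assumptions. The wording of the urgent-decision exception makes a link to progression plausible for that group, so the likely direction is upward. The documents do not establish that the results are biased.

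A reader might also convert the shares into inflated medians with the constant-hazard factor 1/(1 − f), that is 1.11, 1.25 and 1.43 for 10%, 20% and 30%. That ignores the scan schedule, on which Kaplan-Meier medians move in whole intervals. In the simulation, an assumed median of 9 months is read as 9 months without switching, 12 months at 10% or 20%, and 18 months at 30%. An assumed median of 12 months is read as 18 months throughout.

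**What to change.** - Keep the present PFS and DoR rules as the main analysis. Limiting the main analysis to scans before new therapy would discard later IRC progressions that now count as events.
- Add one sensitivity analysis for IRC-based PFS and one for DoR. In each, new anticancer therapy started before IRC progression is an event on its start date. The missed-assessment rule must not undo this: a death after new therapy is not to be censored because scans were missed.
- For best response (ORR and CRR), count only IRC assessments dated on or before the start of new therapy.
- Report, by regimen, how many patients started new therapy before IRC progression.

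Counting switches as events is too severe if switching is unrelated to progression, so this belongs in a sensitivity analysis and should be read alongside the main result.

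**Cost.** Merge one dataset that is already supplied and repeat two tables. The sensitivity estimates may be less favourable. If few patients switched, the same tables will show that the main results are robust.

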3.7.4.1.1 Analysis

The following will be presented by dosing regimen.

- The number of participants included in the analysis, those with event and those who are censored.
- The estimate of the median, 25th and 75th percentiles for progression free survival time
- The progression free survival rate at 3, 6, 9, 12 and 15 months.

The corresponding KM plot of the probability of being progression free against time will also be presented.

3.8 Safety Analyses

3.8.1 Adverse Events

Adverse events (AEs) will be coded using the MedDRA dictionary version utilised for Part A. All patients included in Parts B and C of the study will be included in the AE tables.

The start of the AE reporting for a study participant will coincide with signing of informed consent.

Where AE severity is recorded instead of AE Common Terminology Criteria for Adverse Events (CTCAE) grade, this will be mapped to the corresponding CTCAE grade for summary purposes using CTCAE v4.0. AEs recorded as Mild will be mapped to Grade 1, Moderate to Grade 2, Severe to Grade 3, Life-threatening to Grade 4 and Death to Grade 5. AE severity will not be reported.

Although there is an AESI eCRF page, a clinical review of the unique MedDRA coded terms will also be conducted by the sponsor to identify any further applicable AESIs.

3.8.1.1 Treatment-Emergent Adverse Events

The focus of AE summarisation will be on treatment-emergent adverse events (TEAE).

Treatment-emergent adverse events AEs (TEAEs) are defined as those adverse events (AEs) occurring after first administration of rituximab or starting prior to the first administration and worsening during treatment. Adverse events with unknown onset date/time will be considered to be treatment-emergent unless the stop date/time is known to be before first administration of rituximab.

A treatment related TEAE is defined as a TEAE that is possibly or probably or definitively/certainly related to the study treatment (Betalutin, rituximab or lilotomab). If the TEAE has a missing relationship it is assumed to be related to the study treatment for analysis

purposes. This will also be derived separately for Betalutin, rituximab and lilotomab. If the TEAE has a missing relationship it is assumed to be related to all applicable study treatments for analysis purposes.

AEs will be classed as occurring in one of five periods:

- Pre-treatment - any AE that starts after the participant has provided written informed consent and that resolves prior to the first administration of rituximab, or an AE that starts prior to the first administration of rituximab and does not increase in severity after the first administration of rituximab.
- Baseline Period: any AE that starts after the participant has the first administration of rituximab but prior to the first administration of lilotomab or Betalutin (study Day 1).
- Lilotomab/Betalutin Exposure Period: any AE that occurs after the first administration of lilotomab or Betalutin (study Day 1) and upto, and including Day 92, or that is present prior to the first administration of lilotomab or Betalutin and worsens after the first administration of lilotomab or Betalutin.
- Rituximab Exposure Period: relates to the combined Baseline Period and Lilotomab/Betalutin Exposure Period (i.e. all AEs that start after the first administration of rituximab).
- Post Betalutin follow-up period: any AE which starts more than 92 days after the start of Betalutin.

All pre-treatment AEs will be excluded from the tabulations but will be fully listed.

